3.0 TRIAL OBJECTIVES

Primary Objective.

- For the initial phase. To determine the safety and tolerability of the combination of nivolumab and plinabulin.
- For the subsequent phase. To determine the overall response rate (ORR) of treatment with nivolumab with the addition of plinabulin in the treatment of advanced stage non-small cell lung cancer in the second line setting.

Secondary Objectives.

- To determine the progression free survival (PFS), disease control rate (DCR), Duration of Response (DOR) and overall survival (OS) of patients treated with nivolumab in combination with plinabulin.
- To determine the safety and tolerability of the combination of plinabulin and nivolumab.

Translational objectives.

- Patients who have pre-treatment and/or post cycle one biopsy will have flow cytometry of their tissue to identify infiltration of immune cells, rates of expression of PD-1, PD-2 and PDL1. In partnership with [name], we will correlate the percentage and characteristics of immune cells with response to therapy.

4.0 STUDY POPULATION AND SELECTION OF SUBJECTS.

Inclusion criteria

Patients must meet the following criteria to be eligible to participate in the current study:

1. Subjects must have histologically or cytologically-documented stage IIIB or stage IV, recurrent, or metastatic NSCLC.
2. Subjects must have received prior platinum doublet based treatment.
 - Up to 2 lines of prior systemic therapy for metastatic disease are permitted.
 - Adjuvant chemotherapy or concurrent chemoradiation for early stage disease does not count as prior therapy unless subject progressed within 6 months of completion of regimen
 - Patients with known activating mutations in EGFR, or known translocation in ALK or ROS-1 are eligible provided they have progressed on or were intolerant to FDA approved targeted therapy.
3. Subjects must be ≥ 18 years of age.
4. Subjects must have an Eastern Cooperative Oncology Group (ECOG) performance status of 0 to 2.
5. Subjects, including those in the dose-escalation portion of the study, must have measurable disease per RECIST 1.1 criteria. Imaging must be within 28 days of trial enrollment.
 - Target Lesions may be located in a previously irradiated field if there is documented (radiographic) disease progression in that site prior to trial enrollment
6. Subjects must have organ and marrow function as follows:
 - Absolute neutrophil count (ANC) $\geq 1000/\text{mm}^3$,

- Platelets $\geq 75,000/\text{dL}$,

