All subjects who sign consent to participate in this trial will undergo a mandatory biopsy prior to the start of treatment and after 1 cycle of treatment. The biopsy is mandatory but the treating physician must deem the biopsy feasible and safe; if the physician feels that the biopsy is not feasible or it is not safe the subject will still be allowed to enroll in trial. The biopsy will take place at baseline after eligibility criteria has been confirmed and after the first cycle. Tumor tissue samples consisting of core needle biopsies of deep tumor tissue or lymph nodes or excisional, incisional, punch, or forceps biopsies of cutaneous, subcutaneous, or mucosal lesions will be obtained. Fine needle aspirates, cell pellets from effusions or bone biopsies are not permitted. Target lesions considered for core needle biopsies should be deemed suitable for retrieval of at least three cores (minimum diameter 18- gauge). The biopsy will be delivered to the laboratory of [name].

Treatment on Days 1 and 15 of each Cycle.

Cycles are defined as 28 days.

- On Days 1 and 15 of each cycle (+/- 2 days), the following will be performed prior to therapy administration:
 - History and physical examination that includes examination of major organ systems, ECOG performance status (Days 1 only), weight (Days 1 only), vital signs, adverse event evaluation
 - Laboratory evaluations (Days 1 only) including:
 - CBC with differential
 - Serum Chemistry (sodium, potassium, chloride, carbon dioxide, creatinine, BUN, glucose, calcium, albumin, bilirubin, AST, ALT, total protein, and alkaline phosphatase)
 - Thyroid function (TSH, T3, Free T4) will be performed on Day 1 of every ODD cycle

Drug Administration

6.1.1 Dose calculation.

Plinabulin doses will be determined by the patient's actual weight on Day 1 of each cycle, Nivolumab doses are fixed at a flat dose of 240mg.

6.1.2 Schedule of administration.

Patients will receive therapy on days 1 and 15 of a 28 day cycle. Therapy will consist of plinabulin administered via intravenous infusion (IV) over 30 minutes (+/- 5 minutes) followed by nivolumab administered via intravenous infusion (IV) over 60 minutes (+/- 10 minutes).

- Cycles one and two require a 1-hr observation period between plinabulin and nivolumab administration. No observation period will be required in subsequent cycles if infusions were tolerated without any infusion reactions.

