Patients who discontinue treatment without receiving study medication will be replaced. No other patients will be replaced

Clinical Study Protocol 9602
Drug Substance: plinabulin
IND: 129799
Protocol v5.1
Date 7/15/2017

Schedule of events

	Screening ¹	Cycle 1		Cycle 2+		Off Study ¹²	Survival follow up
		Day 1 +/- 2 days	Day 15 +/- 2 days	Day 1 +/- 2 days	Day 15 +/- 2 days		
Informed consent ²	X						
Demographics	X						
Medical history	X						
Concurrent meds	X	X	X	X	X	X	
Physical exam	X	X	X	X	X	X	
Adverse event evaluation		X	X	X	X	X	X ¹³
Vital signs ³	X	X ¹⁴	X ¹⁴	X ¹⁴	X ¹⁴	X	
Height, weight ⁴	X	X		X		X	
Performance status	X	X		X		X	
Biopsy ⁵	X			X			
CBC w/differential	X	X		X		X	
Serum chemistry ⁶	X	X		X		X	
Thyroid Function ⁷	X	X		X ⁷			
Serum pregnancy test	X ⁸						
Disease assessment (CT scan) ⁹	X			8 (±1) weeks, starting in C7 12 (±1) weeks ¹⁰		X	
Brain CT or MRI	X ¹¹	As clinically indicated					
Survival assessment							X
Plinabulin		X	X	X	X		
Nivolumab		X	X	X	X		

1: screening evaluations must be performed within 28 days of Cycle 1 Day 1
2: consent must be performed prior to initiation of any screening or study-specific procedures

Clinical Study Protocol 9602
Drug Substance: plinabulin
IND: 129799
Protocol v5.1
Date 7/15/2017

- 3: vital signs should include: temperature, blood pressure, heart rate, and respiratory rate
- 4: height is needed at screening only
- 5: biopsy is mandatory for all subjects if treating physician deems it to be safe and feasible. If treating physician deems biopsy not safe and/or not feasible the subject may still be enrolled if they meet all other inclusion criteria.
- 6: sodium, potassium, chloride, carbon dioxide, creatinine, BUN, glucose, calcium, albumin, total bilirubin, AST, ALT, total protein, and alkaline phosphatase
- 7: TSH, T3, Free T4 will be performed at screening and Day 1 of every ODD cycle
- 8: serum pregnancy test (for women of childbearing potential only). Subjects must use an acceptable method of birth control.
- 9: CT scan scan of known sites of involvement. A prior CT scan that is no more than 28 days before the initiation of treatment may be used.
- 10: disease will be assessed 8 (\pm 1) weeks, after cycle 7 patients will be reimaged every 12 (\pm 1) weeks.
- 11: brain CT or MRI does not need to be repeated if scans were performed within 28 days of C1D1
- 12: off-study evaluation will be performed within 28 days (\pm 7 days) after last dose of study treatment

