7.4 Plinabulin

Dose delay and/or dose reduction of plinabulin should be considered for significant tumor pain, hypertension, or constipation (including ileus). As a single agent, plinabulin has not been associated with severe hematological toxicity. If a patient experiences a Grade 3 or 4 non-hematologic AE related to plinabulin or the combination of plinabulin with nivolumab, OR requires more than a 14-day delay of scheduled treatment due to toxicity related to plinabulin, regardless of severity, the dose of plinabulin will be reduced per Table 2.

If the same toxicity with same or higher severity recurs despite dose reduction, plinabulin will be discontinued and the patient will continue receiving nivolumab alone. Only one dose reduction for plinabulin is permitted. See [Table 2](#) Dose Modification for Plinabulin.

Treatment with plinabulin will be discontinued permanently for a concomitant elevation of aspartate aminotransferase (AST) or alanine aminotransferase (ALT) levels of more than 3 times the institutional upper limit of normal and bilirubin levels of more than 2 times the institutional upper limit of normal.

Table 2. Dose Modification for Plinabulin.

Condition	Action
First Occurrence of grade 3 or 4 non-hematologic AE assessed as possibly, probably or definitely related to plinabulin	Reduce plinabulin by 10 mg/m ² on subsequent administrations
Second occurrence of Grade 3 or 4 non-hematologic AE assessed as as possibly, probably or definitely related to plinabulin	Discontinue plinabulin (patients may continue on nivolumab alone)
AST and/or ALT > 3 x ULN AND total bilirubin > 2 x ULN assessed as as possibly, probably or definitely related to plinabulin	Discontinue plinabulin (patients may continue on nivolumab alone)

8.0 SAFETY PARAMETERS AND DEFINITIONS:

8.1 Adverse Events:

Adverse events will be collected after the patient has taken the first dose of study drug. After discontinuation from treatment, patients must be followed for all existing AEs for 28 calendar days after the last dose of study drug or until another anti-cancer therapy is initiated.

Clinical Study Protocol 9602
Drug Substance: plinabulin
IND: 129799
Protocol v5.1
Date 7/15/2017

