8.2 Serious Adverse Events: (Immediately Reportable to the Sponsor and BeyondSpring)

An adverse event or suspected adverse reaction is considered "serious" (SAE) if, in the view of either the investigator or sponsor, it results in any of the following outcomes: Death, a life-threatening adverse event, inpatient hospitalization or prolongation of existing hospitalization, a persistent or significant incapacity or substantial disruption of the ability to conduct normal life functions, or a congenital anomaly/birth defect. Important medical events that may not result in death, be life-threatening, or require hospitalization may be considered serious when, based upon appropriate medical judgment, they may jeopardize the patient or subject and may require medical or surgical intervention to prevent one of the outcomes listed in this definition. In the event of an SAE, regardless of suspected causality, occurring after the patient has initiated study therapy and until 28 days after the patient has stopped study treatment must be reported to the sponsor and BeyondSpring within 24 hours of learning of its occurrence. Any SAEs experienced after this 28-day period should only be reported to the sponsor if the investigator suspects a causal relationship to the study drug exists.

Deaths attributed to disease progression do not need to be reported as an SAE regardless of when they occur.

IND safety reports will be submitted to the FDA in compliance with 21 CFR 312.32.

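### The baseline research biopsy precedes the first dose, but AE and SAE collection starts at the first dose, so its harms are not systematically captured

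*Combined protocol and SAP*

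**What the plan says.** **The biopsy.** Section 6.0 (Biopsy) states that "All subjects who sign consent to participate in this trial will undergo a mandatory biopsy prior to the start of treatment", with a second biopsy after cycle 1. On timing: "The biopsy will take place at baseline after eligibility criteria has been confirmed and after the first cycle". There is a waiver: "if the physician feels that the biopsy is not feasible or it is not safe the subject will still be allowed to enroll in trial". Footnote 5 of the schedule of events repeats it. Permitted samples are "core needle biopsies of deep tumor tissue or lymph nodes or excisional, incisional, punch, or forceps biopsies of cutaneous, subcutaneous, or mucosal lesions", and lesions considered for core needle biopsy should be able to yield at least three cores of 18 gauge or larger. The purpose is translational. Section 3.0 says: "Patients who have pre-treatment and/or post cycle one biopsy will have flow cytometry of their tissue".

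**The collection window.** Section 8.1: "Adverse events will be collected after the patient has taken the first dose of study drug". Footnote 13 of the schedule also starts AE recording at the first administration of investigational drug. Section 8.2 limits the 24-hour SAE duty to events "occurring after the patient has initiated study therapy and until 28 days after the patient has stopped study treatment". The schedule marks the biopsy at screening but marks no adverse event evaluation there.

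**What goes on the CRF.** Sections 7.0 and 8.1 require recording of AEs that interrupt treatment or reduce the dose, and of drug-related AEs of Grade 2 or higher. The five attribution categories in section 7 are all defined by the relation to the study drug or its administration.

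**Patients never dosed.** Section 6 (Replacement of patients): "Patients who discontinue treatment without receiving study medication will be replaced". The analysis population in section 9.2 requires treatment at the MTD and at least one dose.

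**The concern.** The biopsy is a risk that the trial itself imposes, for research purposes, on patients already found eligible. It is the one invasive study procedure before dosing, and it falls in an interval for which the protocol sets no AE or SAE window. If a complication occurs there, no rule requires it to be graded, attributed to the biopsy or sent to the sponsor within 24 hours. If it keeps the patient from being dosed, the replacement rule and the section 9.2 population together mean that no planned summary would show it.

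What is at stake is oversight of the procedure. Without systematic capture, those monitoring the trial lack a count from which to judge whether the biopsy requirement is causing harm or costing enrolled patients their treatment. A safety report that followed the rules as written would contain no AE attributed to the baseline biopsy, whatever had happened.

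**Working it through.** **1. Order of events.** Sections 6.0 and 8 together give: consent, eligibility confirmed, baseline biopsy, first dose, start of AE and SAE collection. Section 8.1, section 8.2, footnote 13 and the schedule table agree on the starting point, so this is a consistent rule and not a slip in one sentence. No section sets a separate window for procedure-related events between consent and first dose.

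**2. Provisions not tied to the first dose.**
- Section 8.1 has site staff note each patient's medical conditions before treatment. It asks for no attribution to the biopsy and no sponsor report, and a complication noted there becomes part of the baseline.
- Section 7.0 has the investigator alert the IRB to events that seem unusual. A recognised biopsy complication may not seem unusual, and the alert goes to the IRB, not to the sponsor.
- Section 8.3 makes the PI responsible for AE reporting according to the protocol's guidelines, which leads back to the same window. It also calls for appropriate reporting of adverse reactions that raise safety concerns, but sets no window, grading or form for this.

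**3. The post-cycle-1 biopsy.** This one lies inside the window. SAEs are reportable regardless of causality (section 8.2). A non-serious complication must go on the CRF only if it is Grade 2 or higher and related to study medication, or if it interrupts treatment or reduces the dose. A non-serious Grade 2 or 3 complication judged unrelated to the drug, with dosing unchanged, need not be entered.

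**4. Illustrative size.** The documents give no complication rate, so the rate q is an assumption. The stated total is n = 33 + 6 = 39 (section 9.1). Taking n = 33 shows the effect of six fewer biopsies, for example through waivers. Expected events = n × q. Chance of at least one = 1 − (1 − q)^n, assuming independent patients with equal risk.

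| Assumed q | Expected, n = 39 | At least one, n = 39 | Expected, n = 33 | At least one, n = 33 |
|---|---|---|---|---|
| 1% | 39 × 0.01 = 0.4 | 32% | 0.3 | 28% |
| 5% | 39 × 0.05 = 2.0 | 86% | 1.7 | 82% |
| 10% | 39 × 0.10 = 3.9 | 98% | 3.3 | 97% |
| 20% | 39 × 0.20 = 7.8 | over 99% | 6.6 | over 99% |

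Waivers lower n. Replaced patients who had already been biopsied raise it.

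**5. The plan's own design figures.** The point does not rest on these, but they were checked. The design stops at 4 or fewer responses in 18 and rejects the null at 11 or more in 33. The probability of rejection is the sum over k = 5 to 18 of P(X1 = k) × P(X2 ≥ 11 − k), with X1 binomial on 18 patients and X2 on 15. This gives a type I error of 0.0458 at a 20% response rate and power of 0.8011 at 40%. The early-stopping probabilities are 0.716 and 0.094. All agree with section 9.1 (.05, 0.8, 0.72, 0.09), and changing the AE window alters none of them.

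**The case against.** The strongest reply is that the safety objective concerns the tolerability of the drug combination. Pre-dose biopsy events cannot inform that, and response rate is untouched. This stands: no conclusion about the drugs changes. It does not answer the point, which is oversight of a procedure that the trial imposes.

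A second reply is that biopsy risk is already controlled. The physician may waive the biopsy, and punch, forceps, incisional or excisional sampling of accessible lesions is allowed. This also stands, and it limits how many patients are exposed. But the waiver is a judgement made beforehand and records nothing about the outcome when a biopsy is done.

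Third, a reader might infer that baseline biopsy harms are never recorded or reported, or that the PI, sponsor and DSMC could not learn of them. The documents do not support that. The pre-treatment note and the IRB alert are partial routes, the phase 2 portion is single-center, and the investigator is responsible for patients' medical care. IRB policy and the Consortium monitoring plan, which are not among the documents, may add requirements. The gap is in systematic capture and sponsor reporting.

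Fourth, a reader might take replacement to mean that a harmed patient is dropped from care. The replacement rule concerns sample accounting, and section 7.0 keeps the investigator responsible for care.

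Finally, it would be too strong to say that non-serious complications of the second biopsy go unrecorded. Site staff note any AE, and only CRF entry is filtered. Some such events might also be judged possibly drug-related under the section 7 definitions.

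**Conclusion.** The concern holds as a gap in systematic safety capture. Between consent and first dose, the protocol imposes a research biopsy, subject to the physician's waiver, and provides no AE or SAE window for its harms. A patient who cannot be dosed because of a complication is replaced and is outside the stated analysis population. For the second biopsy the gap is narrower and concerns CRF entry of non-serious events only.

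The size cannot be fixed from the documents. With 39 biopsied patients, the expected number of events outside the window runs from 0.4 at an assumed 1% to 7.8 at an assumed 20%. The result rests on reading the protocol alone, without the IRB policy or the monitoring plan to which it defers. It is a worthwhile and inexpensive correction to safety oversight, with no effect on the efficacy analysis or the Simon design.

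**What to change.** - In sections 8.1 and 8.2 and in footnote 13, collect AEs and SAEs related to protocol-mandated procedures from signed consent. Leave all other AEs starting at first dose, as now.
- Add an adverse event check to the schedule for the interval between the baseline biopsy and the first dose. The existing Day 1 pre-dose visit can serve for patients who go on to treatment.
- Add study procedure as an attribution option beside the drug-related categories in section 7, and require CRF entry of procedure-related events of Grade 2 or higher. This also closes the gap for the second biopsy.
- In section 9, list procedure-related events for all biopsied patients, including those never dosed and replaced, and give the number biopsied as the denominator.

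The cost is protocol wording, one extra CRF option and a short listing. No extra visits or procedures are needed for patients who are dosed, and the sample size and decision rules stay as they are.

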8.2 Serious Adverse Events: (Immediately Reportable to the Sponsor and BeyondSpring)

An adverse event or suspected adverse reaction is considered "serious" (SAE) if, in the view of either the investigator or sponsor, it results in any of the following outcomes: Death, a life-threatening adverse event, inpatient hospitalization or prolongation of existing hospitalization, a persistent or significant incapacity or substantial disruption of the ability to conduct normal life functions, or a congenital anomaly/birth defect. Important medical events that may not result in death, be life-threatening, or require hospitalization may be considered serious when, based upon appropriate medical judgment, they may jeopardize the patient or subject and may require medical or surgical intervention to prevent one of the outcomes listed in this definition. In the event of an SAE, regardless of suspected causality, occurring after the patient has initiated study therapy and until 28 days after the patient has stopped study treatment must be reported to the sponsor and BeyondSpring within 24 hours of learning of its occurrence. Any SAEs experienced after this 28-day period should only be reported to the sponsor if the investigator suspects a causal relationship to the study drug exists.

Deaths attributed to disease progression do not need to be reported as an SAE regardless of when they occur.

IND safety reports will be submitted to the FDA in compliance with 21 CFR 312.32.

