5.1.4 Second Phase

In the second phase of the study patients will receive plinabulin at the MTD identified previously and nivolumab 240 mg on the same day and repeated every 2 weeks. Re-staging studies will be conducted every 8 (+/-1) weeks, after cycle seven scans will be done every 12 (+/-1) weeks. Those who achieve a complete response, partial response, or stable disease will continue on study. Will use RECIST 1.1 criteria to determine response to treatment. Patients with progressive symptomatology and progressive disease seen in imaging studies will be taken off study. To account for pseudo-progression, in the case of progressive disease in the absence of worsening symptomatology, at the discretion of the treating physician, a patient will be allowed to continue receiving treatment for 2 more cycles followed by restaging studies. If progressive disease is confirmed the patient will be taken off study.

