6.6 Tumor Evaluations

CT scan of all known areas of disease with tumor evaluation using RECIST 1.1 and IrRC criteria will be performed every 8 (+/-1) weeks. After 7 cycles of therapy, imaging studies will be performed every 12 (+/- 1) weeks.

- Patients who have a CR, PR, or SD may continue on study per study protocol.
- If progressive disease is documented the patient may remain on study provided:
 - The patient does not have clinical signs or symptoms of tumor progression
 - No decline in ECOG performance status
 - Absence of progressive tumor at critical anatomic sites (i.e. spinal cord compression).
 - Treating physician believes that the patient continues to derive clinical benefit from study treatment
 - Repeat imaging scans should be repeated ≥ 4 weeks (+/- 7 days) after documented progression. If progression is confirmed the subject will be removed from study.

Off Study Visit.

Patients will undergo the following assessments 28 days (+/- 14 days) after last dose of study treatment

- History and physical examination that includes examination of major organ systems, ECOG performance status, weight, vital signs, adverse events assessment
- Laboratory evaluations including:
 - CBC with differential
 - Blood chemistry (sodium, potassium, chloride, carbon dioxide, creatinine, BUN, glucose, calcium, albumin, bilirubin, AST, ALT, total protein, and alkaline phosphatase)

Permitted medications

All treatments that the investigator considers necessary for a subject's welfare may be administered at the discretion of the

investigator in keeping with the community standards of medical care.

If an increase in systolic blood pressure to > 160 mmHg is observed after administration of plinabulin, oral amlodipine 10 mg or an equivalent calcium channel blocker should be administered before each subsequent dose. Increases in systolic blood pressure above 200 mmHg should be managed with nitroprusside or similar regimen per institutional practice.

Dexamethasone may be used as either a pre-medication or as a rescue medication for patients that experience plinabulin-related nausea and vomiting that is not controlled adequately with a 5HT3 agonist (e.g. ondansetron) alone

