7.1 Definition of Dose-Limiting Toxicities (DLT)

A DLT is defined as one of the following adverse events reported during the DLT observation period, if considered to be definitely, probably, or possibly related to either study regimen by the investigator; and fulfills any one of the following criterion using NCI CTCAE Version 4.0:

1. Nonhematologic toxicity as follows:

- a) Grade 4 nonlaboratory toxicity
- b) Grade 3 nonlaboratory toxicity (for example, nausea, vomiting, and diarrhea) lasting >3 days despite optimal supportive care.
- c) Any Grade 3 or Grade 4 laboratory value if:
 - i) Medical intervention is required to treat the patient, or ii)
The abnormality persists for >1 week.

Note: Liver function abnormality: For patients with liver metastasis who begin treatment with Grade 2 aspartate aminotransferase (AST) or alanine amino transferase (ALT), if AST or ALT increases by greater than or equal to 50% relative to baseline and lasts for at least 7 days

2. Hematologic toxicity, as follows:

- a) Grade 4 thrombocytopenia and Grade 4 anemia.
- b) Other grade 4 toxicities lasting ≥ 7 days, or
- c) Grade 3 thrombocytopenia if associated with bleeding and requires platelet transfusion, or
- d) Febrile neutropenia Grade 3 or Grade 4

3. Any grade 5 toxicity

4. Any other significant toxicity deemed by the primary investigator and the sponsor to be dose limiting, for example:

- a) Any toxicity that is possibly related to study treatment that requires the withdrawal of the patient from the study
- b) A delay of > 14 days due to persistent Grade ≥ 2 toxicities in initiating the subsequent cycle, with the exception of Grade 2 fatigue

Any infusion or hypersensitivity reactions occurring during the infusion of the drug are not considered dose-related and therefore will NOT be considered to be a DLT.

Attribution of adverse events.

Unrelated: This relationship suggests that there is no association between the study drug and the reported event.

Unlikely: This relationship suggests that the association between the study drug and the reported event is unlikely.

Possible: This relationship suggests that treatment with the study drug caused or contributed to the AE, ie, the event follows a reasonable temporal

sequence from the time of drug administration or follows a known response pattern to the study drug, but could also have been produced by other factors.

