Prior to beginning study treatment, study site personnel will note the occurrence and nature of each patient's medical condition(s). During the study, site personnel will again note any change in the condition(s) and/or the occurrence and nature of any adverse events. Toxicities are to be graded according to the NCI CTC version 4.0.

A description of the event, including its date of onset and resolution, any action taken should be provided along with the investigator's assessment of causality. An event that is due to unequivocal progression of disease should not be reported as an AE. Any adverse events leading to a treatment interruption or dose reduction along with all grades 2 and higher adverse events related to study medication must be recorded on a case report form (CRF).

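### Section 8.2 waives SAE reporting for any death attributed to progression, a looser test than section 8.1 sets and at odds with 8.2's own 24-hour rule

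*Combined protocol and SAP*

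**What the plan says.** Section 8.2 lists death among the outcomes that make an event serious. Its reporting rule begins "In the event of an SAE, regardless of suspected causality, occurring after the patient has initiated study therapy", runs until 28 days after treatment stops, and requires that such events "must be reported to the sponsor and BeyondSpring within 24 hours of learning of its occurrence". For SAEs after those 28 days the rule is narrower: they "should only be reported to the sponsor if the investigator suspects a causal relationship to the study drug exists". A separate sentence then makes an exception: "Deaths attributed to disease progression do not need to be reported as an SAE regardless of when they occur". It does not say who makes the attribution, how certain it must be, what must support it, or who checks it.

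Section 8.1 has its own exclusion for progression: "An event that is due to unequivocal progression of disease should not be reported as an AE". It speaks of events in general, so it covers fatal and non-fatal events alike. Section 8.1 also requires case report form entries for related events of grade 2 or higher and for events that lead to interruption or dose reduction.

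Section 7.1 defines a DLT from adverse events in the observation period that the investigator considers at least possibly related. Item 3 of the list is "Any grade 5 toxicity". Section 7.1 makes no reference to SAE reports.

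**The concern.** A death in the reporting window can meet two different tests for the same judgement. If progression is a plausible but not a certain cause, the death falls outside the 8.1 exclusion and remains an adverse event, yet 8.2 lets it go without an SAE report. The most serious outcome thus gets the easier route out of expedited reporting.

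What is at stake is independent scrutiny. Safety and tolerability are the primary objective of phase 1, and the trial is open-label and single-center. The 24-hour SAE report is the only expedited route that the protocol expressly makes independent of the causality judgement. If the investigator attributes a toxic death to progression, the DLT definition does not catch it, because it was judged unrelated, and the waiver means that no SAE report prompts the sponsor to question the label. Section 7.1 item 4 gives the sponsor a part in deciding that a toxicity is dose limiting, but the sponsor can act only on deaths that it hears about.

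**Working it through.** The plan gives no figure on this point. The check is a comparison of its rules, followed by one illustration of cost.

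**1. The two standards.** Section 8.1 requires unequivocal progression. Section 8.2 requires attribution only. A death possibly or probably due to progression passes the second test and fails the first.

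**2. Where the waiver has effect.** After 28 days from the end of treatment, an SAE is reportable only on suspicion of a causal link to study drug. A death put down to progression would usually not be reported then in any case. The waiver therefore matters mainly from first dose to 28 days after treatment, which is the period in which 8.2 otherwise asks for every SAE whatever its suspected cause. That period includes the DLT window.

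**3. What supports the label early on.** Section 5.1.3 sets the DLT window at cycle 1, which is 28 days. It is extended to two cycles (56 days) only if a delayed DLT occurs. Sections 5.1.4 and 6.6 put the first restaging at 8 (±1) weeks, so at day 49 at the earliest (7 × 7). In cycle 1 no scheduled on-treatment scan can support an attribution to progression. Section 9.3 accepts clinical progression as well as radiological progression, so the plan allows progression to be called without a scan.

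**4. What the waiver does to the DLT count.** Directly, nothing. A grade 5 event counts under 7.1 if the investigator judges it at least possibly related. A toxic death judged to be progression is lost at that step, whether or not an SAE form is sent. Deleting the 8.2 sentence alone would not make the death a DLT. It would only bring the death to the sponsor's attention.

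**5. Illustrative cost of reporting every death in the window.** The documents do not give time on treatment, so this rests on assumptions.

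- Medians of 9.2 and 12.2 months: overall survival on nivolumab in the two randomized trials described in section 2.0.
- 39 patients: total sample size in section 9.1.
- Assumed: exponential survival, 30.44 days per month, exactly two cycles of dosing.
- Window: the last dose is on day 15 of cycle 2, which is 28 + 14 = 42 days after first dose. Adding 28 days gives 70 days, or 70 / 30.44 = 2.30 months.

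Probability of death from any cause by day 70 = 1 − 0.5^(2.30 / median):

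- median 9.2: 1 − 0.5^0.250 = 0.159, and 39 × 0.159 = 6.2 deaths;
- median 12.2: 1 − 0.5^0.188 = 0.122, and 39 × 0.122 = 4.8 deaths.

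This gives roughly 5 to 6 deaths from any cause. Some of these are already reportable under 8.2, so the extra forms would be fewer under the same assumptions. Longer treatment lengthens the window and raises the number.

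**The case against.** The strongest reply is that the sentence does little harm, because deaths from progression are expected in this population and other safeguards exist. Several parts of that reply stand.

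- The waiver covers deaths only. A hospitalization or life-threatening event before death is a separate SAE criterion and stays reportable within 24 hours, unless it is itself unequivocally due to progression. A toxic death after an admission may well reach the sponsor that way.
- Deaths from any cause are still recorded for overall survival and PFS (section 9.3). Section 8.3 provides for reporting to the DSMC and for monitors unaffiliated with the conduct of the study.

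These limit the gap but do not close it. The survival endpoints do not examine cause of death. Section 8.3 works from events reported as the protocol directs, so it inherits the waiver, and it does not provide for review of cause of death.

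Three stronger readings are tempting and are not supported.

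- A reader might infer that the waiver drops toxic deaths from the DLT count. It does not: 7.1 does not depend on SAE reporting (step 4 of the working).
- A reader might use the pseudo-progression provisions, "To account for pseudo-progression, in the case of progressive disease in the absence of worsening symptomatology" in 5.1.4 and "If progressive disease is documented the patient may remain on study provided" in 6.6, to argue that attribution is unreliable in the DLT window, or that almost any respiratory death could be put down to progression. Treatment past a scheduled scan showing progression falls essentially after the 28-day window. Section 6.6 also limits it to patients without clinical signs or symptoms of progression, without ECOG decline and without progression at critical sites. The documents do not support so broad a statement about respiratory deaths.
- A reader might compute the chance of a death in a cohort's DLT window and take it as the rate of missed DLTs. That would count deaths from every cause.

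**Conclusion.** The conflict is real and rests on the text alone: 8.1 and 8.2 apply different tests to progression, and the 8.2 waiver contradicts the cause-neutral 24-hour rule in the same section. The consequence is limited. A misattributed toxic death *could* miss expedited sponsor review, including in cycle 1. It is not shown that any would, and the waiver does not alter the DLT count by itself. How often this would happen cannot be derived, because the documents give no misattribution rate. The figure of 5 to 6 deaths describes the reporting load under assumed exponential survival and two cycles of dosing. It does not measure harm. The change is worth making because it is cheap and restores a check on the attribution where the plan provides no other.

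**What to change.** 1. **Section 8.2.** Replace the waiver with wording to this effect: *All deaths from first dose to 28 days after the last dose are reported to the sponsor and BeyondSpring within 24 hours, with cause and attribution. After that period, only deaths due to unequivocal progression are exempt.* This brings the later exemption into line with 8.1. The existing rule for SAEs after 28 days can stay.
2. **Section 7.1.** Add that any death in a phase 1 DLT observation period is reviewed by the principal investigator and the sponsor against item 3 before the cohort is cleared. This step is needed because the change to 8.2 does not reach the relatedness call.
3. **Section 9.2.** List these deaths with their attribution beside the rate of grade 3 or higher toxicity.

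The cost is protocol wording and a small number of additional expedited forms, with no added patients, visits or procedures. The drawback is that some clear progression deaths will also be reported on an expedited basis. How many depends on time on treatment.
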